6.2 Power Analysis for Sample Size

A total of 85 subjects (n = 85) will be enrolled.

[figure not shown]

Figure 1. Power analysis workflow. The first sessions were selected as representative of the study design for the initial power analysis (left). A second set of sessions with the largest difference from the reference device were used in a conservative scenario (right).

A total of 475 subjects out of the 571 in the product development cohort had data collected the IVC App in from the first PR collection and were included in the initial power analysis. Only the first PR sessions were used in order to accurately model the clinical study design, where subjects will have only one IVC App collection. The overall ARMS was 0.9 BPM. The bagging procedure was performed on n sizes ranging from 20 to 100 subjects (Figure 2). At all n sizes in the analysis, the 95th percentile of the confidence intervals was below the target ARMS of 3.0. Thus, n sizes of 20 or greater are powered at 95%.

 INFORMED MINDSET MEDICAL	DOCUMENT VERSION: 3	THIS DOCUMENT SUPERSEDES VERSION: 2	PAGE: 14 OF 15
STATUS: Active	TITLE: Informed Vital Core - Statistical Analysis Plan	IDENTIFICATION: IVC-400-006d	
EFFECTIVE DATE: June 22, 2023	AUTHOR: [name]	APPROVED BY: [name]	

Bootstrapped power

[figure not shown]

Figure 2. Bagging results for sample sizes ranging from 20 to 100. The filled-in squares show the 95th percentile and the open circles show the 90th percentile of the upper bound of the confidence intervals. The x-axis shows the sample size of the subsamples and the y-axis is the RMS. All 95th percentiles are below the target ARMS of 3.0.

As well as the first IVC App collection attempt used in the power analysis above, some of the subjects provided additional data collection sessions under varied conditions for product development. To perform a more conservative power analysis, the session with the largest absolute difference from the reference device was selected for each subject. The same bagging analysis over 484 “worst case” collections with an ARMS of 1.5 BPM showed 90% power with 40 subjects and 95% power with 45 subjects. The conservative power analysis was used to establish a PP group goal of 55 subjects to ensure that power is at or above 95%. Additionally, a sample size greater than 50 subjects ensures that the sample is likely to be representative of the IVC App performance under the Central Limit Theorem. Since the IVC App is designed to report only reliable results and inform the user that a PR could not be collected otherwise, not all sessions result in a successful PR measurement. As mentioned above, the PR collection rate for the IVC app was 80%, so the study will be overenrolled to reach the target PP group size. A total of 85 subjects will be enrolled, allowing for screening failures, withdrawals, technical failures, and sessions where the IVC App does not report a PR.

In order to ensure a diverse PP group, the enrollment target for the PP group is 15% in the dark (Fitzpatrick 5-6) skin tone group. Initially enrollment will be random, but targeted enrollment may be used to meet skin tone goals if the dark skin tone PP group is projected to fall below the 15% goal.

 INFORMED MINDSET MEDICAL	DOCUMENT VERSION: 3	THIS DOCUMENT SUPERSEDES VERSION: 2	PAGE: 15 OF 15
STATUS: Active	TITLE: Informed Vital Core - Statistical Analysis Plan	IDENTIFICATION: IVC-400-006d	
EFFECTIVE DATE: June 22, 2023	AUTHOR: [name]	APPROVED BY: [name]	

6.3 Safety Analysis

No safety analysis is planned. The IVC App is a remote device so no device related AEs are anticipated.

6.4 Exploratory Analyses

All exploratory analyses will be based on ITC and PP populations.

The scope of this document is limited to determining the heart rate obtained by the Edan SE-301 ECG device used in IVC-400-006 Pulse Rate Clinical Study. This document does not include the procedure for heart rate determination or analysis produced by the IVC App.

3. References

Document Number	Description
IVC-400-006	Informed Vital Core – Clinical Study Protocol
IVC-400-006g	Informed Vital Core – Clinical Study Site Instruction Guide: Pulse Rate

4. Procedure

Heart rate (HR) is calculated using lead-I from a 6-lead ECG taken with the Edan SE-301 (ECG). The ECG unit is configured to conduct a 60 second ECG recording conducted simultaneously with an IVC App PR measurement session. The results of the ECG recording are stored in a standardized XML format and are referred to as the ECG XML Rhythm Strip file(s) (or rhythm strip(s)). Simple averaging over the course of the session is not precise due to natural heart rate variability. In order to achieve high enough precision to validate the accuracy of the IVC App, the inter-session heart rate must match the measurement times reported by the ECG device.

A Python script (or script) reads the ECG XML Rhythm Strip files, aligns the data collection windows, and performs the heart rate analysis; calculating a heart rate that is accurately synchronized to the IVC App data collection window. The heart rates produced from the rhythm strip by the Python script will be used as the reference for the primary endpoint analysis.

 INFORMED MINDSET MEDICAL	DOCUMENT VERSION: 1	THIS DOCUMENT SUPERSEDES VERSION: X	PAGE: 4 OF 18
STATUS: Active	TITLE: Rhythm Strip Analysis Procedure for IVC-400-006	IDENTIFICATION: IVC-400-006i	
EFFECTIVE DATE: May 30, 2023	AUTHOR: [name]	APPROVED BY: [name]	

The Python script has been validated on stable releases of standard publicly available libraries and runs in a virtual environment configured from a requirements text file that lists the specific packages and versions (Xie, et. al., 2023). Heart rate analysis is performed using the WFDB package described in Waveform Database Software Package (WFDB) for Python (version 4.1.0). The SHA # will be documented on the Rhythm Strip Analysis Report (RSAR). Validation of the procedure in Section 4.1 and 4.2 will be outlined in Appendix B.

4.1. General Procedure for Collecting ECG Rhythm Strip XML File

1. After the ECG measurement has been collected from the subject per the clinical study protocol, the clinical site staff will upload the ECG Rhythm Strip XML File to a shared drive per the IVC-400-006g Pulse Rate Clinical Study Site Instruction Guide.
2. The subject ID will be on the ECG Rhythm Strip XML file and the file will be copied by Mindset Medical staff to a file folder on SharePoint.
3. The Rhythm Strip Analysis Report will be stored on SharePoint.
4. The ECG Rhythm Strip XML files and Heart Rate Analysis Reports will be stored per 21 CFR 812.140 (b), (d), and (e) when the trial is complete.

4.2. Rhythm Strip Analysis of Electrocardiogram Signal for Reference Heart Rate

Steps involved for the Mindset Medical staff in generating the reference heart rate are listed below:

1. Access the ECG Rhythm Strip XML file from the SharePoint folder.
2. Download the metadata file produced by the IVC App.
3. Run the Python Script on the XML file and the IVC App metadata file. The script can be run from the command line in a Python virtual environment that enforces the version control with arguments that point to the ECG XML Rhythm Strip file and the IVC App metadata file. The Python script performs the following steps:
 - a. Read the ECG Rhythms Strip XML file and return the lead-I signal in millivolts at a 1 kHz sample rate.
 - b. Adjust for the 2.3 second buffer delay added by the Edan SE-301 to synchronize timing with the reference device clock.
 - c. Apply the WFDB XQRS peak detection algorithm.
 - d. Plot and save the ECG signal with peak markers for visual validation.
 - e. Compute the moving average heart rate (HR-MA) by using a sliding window of 12 RR-intervals. Boundary values are imputed using expanding windows.
 - f. Sample the HR-MA at the solution times reported by IVC App metadata and average.

 INFORMED MINDSET MEDICAL	DOCUMENT VERSION: 1	THIS DOCUMENT SUPERSEDES VERSION: X	PAGE: 5 OF 18
STATUS: Active	TITLE: Rhythm Strip Analysis Procedure for IVC-400-006	IDENTIFICATION: IVC-400-006i	
EFFECTIVE DATE: May 30, 2023	AUTHOR: [name]	APPROVED BY: [name]	

4. Visual validation of the Rhythm Strip Analysis Report is performed by two Mindset Medical reviewers. The first review is the primary reviewer and the second reviewer will perform a quality control review.
 - a. Discrepancies identified will be documented and reviewed by management for inclusion or exclusion in the final analysis.
5. The result is a single integer value for reference heart rate that is entered into the study electronic data capture system.

Note: The script will warn if there is a timing discrepancy or if the reference range violates the study protocol which can be included in the notes field.

 INFORMED MINDSET MEDICAL	DOCUMENT VERSION: 1	THIS DOCUMENT SUPERSEDES VERSION: X	PAGE: 6 OF 18
STATUS: Active	TITLE: Rhythm Strip Analysis Procedure for IVC-400-006	IDENTIFICATION: IVC-400-006i	
EFFECTIVE DATE: May 30, 2023	AUTHOR: [name]	APPROVED BY: [name]	

5. References

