STATUS: Active	TITLE: Informed Vital Core –Clinical Study Instruction Guide: Pulse Rate	IDENTIFICATION: IVC-400-006g	16 OF 25
EFFECTIVE DATE: April 5, 2023	AUTHOR: [name]	APPROVED BY: [name]	

Step	Task
	
8.	
Verify that the electrodes on the subject are still in place and securely attached with both arms resting on the table. Verify that the IVC App is displayed and the phone is placed in the phone stand and in front of the subject.
 
Press the START button on the IVC App and the PRINT/START button on the ECG at the exact same time.
  
NOTE: It is important that both buttons are pressed at the same time. If they aren't, stop the session by closing the browser on the phone and stopping the ECG device, and restart (close the browser tab and return to step 2).

9.	
AUTO Sampling is displayed on the ECG screen while the ECG is measuring the subject's heart rate.
 
10.	When the IVC App measurement session is complete, a pulse rate measurement is displayed.

 INFORMED MINDSET MEDICAL	DOCUMENT VERSION: 1	THIS DOCUMENT SUPERSEDES VERSION: X	PAGE:
STATUS: Active	TITLE: Informed Vital Core –Clinical Study Instruction Guide: Pulse Rate	IDENTIFICATION: IVC-400-006g	17 OF 25
EFFECTIVE DATE: April 5, 2023	AUTHOR: [name]	APPROVED BY: [name]	

Step	Task
	 
Record the subjects pulse rate in the EDC and then tap the SUBMIT RESULTS button.

11.	
When the ECG session is complete and is being saved to the thumb drive automatically, the ECG display will show AUTO Analyzing and then AUTO Sampling. Do not remove the thumb drive while the ECG data is being saved.
 
12.	Return to Section 6 (Sending the IVC App) and repeat Steps 4 and 5 to prepare for the second pulse rate measurement.
13.	Return to the top of Section 7 (Preparing the IVC App for PR Measurement) and repeat Steps 2 – 10 to capture the second IVC PR and the ECG HR.
14.	Proceed to Section 8 (Uploading the ECG Data from the Thumb Drive) to upload the ECG data from the thumb drive.

[figure not shown]
[figure not shown]
8. Uploading the ECG Data from the Thumb Drive

Step	Task
1.	Remove the thumb drive from the back of the ECG machine and insert the USB-A to USB-C adapter (USB-A side).
2.	Insert the USB-C side of the USB-A to USB-C adapter into the mobile phone.

[figure not shown]
[figure not shown]
[figure not shown]
INFORMED MINDSET MEDICAL	DOCUMENT VERSION: 1	THIS DOCUMENT SUPERSEDES VERSION: X	PAGE:

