Appendix A – Readme

- Create venv with Python 3.9.16
- pip install -r requirements.txt
- Run using command below

`python edan_se301_ra.py file_name_ecg file_name_ivc timezone_name`

where timezone_name is US/Pacific or US/Mountain etc. Output prints hr reference value and saves ecg with annotations as pdf

 INFORMED MINDSET MEDICAL	DOCUMENT VERSION: 1	THIS DOCUMENT SUPERSEDES VERSION: X	PAGE: 8 OF 18
STATUS: Active	TITLE: Rhythm Strip Analysis Procedure for IVC-400-006	IDENTIFICATION: IVC-400-006i	
EFFECTIVE DATE: May 30, 2023	AUTHOR: [name]	APPROVED BY: [name]	

[figure not shown]

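### The ECG reference heart rate is stored as a whole BPM with no rounding rule, which usually adds a small, avoidable error to the reported ARMS

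*Combined protocol and SAP*

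**What the plan says.** IVC-400-006i section 4.2 derives the reference heart rate in fine steps. The script is to "return the lead-I signal in millivolts at a 1 kHz sample rate", detect the beats, form a moving average over 12 RR intervals, and then "Sample the HR-MA at the solution times reported by IVC App metadata and average". An average of moving averages is not naturally a whole number. Step 5 nevertheless ends: "The result is a single integer value for reference heart rate that is entered into the study electronic data capture system".

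Section 4 of the same procedure ties this value to the primary analysis: "The heart rates produced from the rhythm strip by the Python script will be used as the reference for the primary endpoint analysis". It explains the time-matched method with the words "In order to achieve high enough precision to validate the accuracy of the IVC App".

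The available text gives no reason for the integer, does not say whether the value is rounded or truncated, and makes no provision to analyse the unrounded value. The eCRF fields for app PR and ECG rate are labelled in bpm, with no statement about decimals.

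SAP sections 3.0 and 5.3.1 judge success by whether the upper 95% confidence limit of ARMS lies below 3.0 BPM. For planning, SAP 6.2 reports for the first sessions: "The overall ARMS was 0.9 BPM". It also gives an ARMS of 1.5 BPM for a worst-case set of sessions, which was used to fix the per-protocol goal of 55.

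**The concern.** ARMS is built from squared differences between the app and the reference, so error in the reference is counted as if it were error in the app. Whole-number reporting by the app, if it does that, belongs to the device under test. Whole-number storage of the reference is an artefact of the study procedure, added after the script has already produced a finer value. The accuracy figure at stake is small (0.9 to 1.5 BPM on the SAP's own data), so a 1 BPM grid on the reference is not trivial beside it. The silence on the rounding rule adds a second issue: truncation is also a way to get an integer, and it would shift every reference value in the same direction.

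**Working it through.** **Inputs.** Reference resolution of 1 BPM (IVC-400-006i 4.2 step 5). ARMS planning values of 0.9 and 1.5 BPM and a per-protocol goal of 55 (SAP 6.2). Limit of 3.0 BPM (SAP 3.0). The 0.9 and 1.5 cannot be reproduced, because the development data from 571 subjects are not given; they are taken as stated.

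**Rounding to the nearest BPM.** Let d be app minus unrounded reference, and r the rounding error, uniform on −0.5 to +0.5. Then E(r) = 0 and E(r²) = 1/12 = 0.0833. If r is independent of d, squared ARMS becomes ARMS² + 1/12.

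| ARMS without reference rounding | Squared | Share added | ARMS with rounding |
|---|---|---|---|
| 0.9 | 0.81 | 0.0833/0.81 = 10.3% | √0.8933 = 0.945 (+5.0%) |
| 1.5 | 2.25 | 0.0833/2.25 = 3.7% | √2.3333 = 1.528 (+1.8%) |
| 3.0 | 9.00 | 0.0833/9.00 = 0.9% | √9.0833 = 3.014 (+0.5%) |

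If 0.9 stands for anything from 0.85 to 0.95, the first share runs from 11.5% down to 9.2%. If the planning values already contain reference rounding, the comparison runs the other way: √(0.81 − 0.0833) = 0.852 and √(2.25 − 0.0833) = 1.472 without it.

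**Check of the independence assumption.** I simulated 2,000,000 pairs with heart rates spread over 50 to 130 BPM. With only the reference rounded, the addition was 0.083 to 0.084 BPM² at ARMS 0.9 under normal, heavy-tailed (t with 3 df) and mixture differences. With the app PR also an integer, it depended on how tightly the bulk of the differences cluster (ARMS about 0.9 throughout):

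- normal differences: 0.083
- 2% large differences, the rest with SD 0.4: 0.079
- 2% large differences, the rest with SD 0.2: 0.038
- 5% large differences, the rest with SD 0.1: −0.008

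The last two arise because app and reference then tend to round to the same integer. These mixtures are illustrative; SAP 6.1 reports high kurtosis but not the distribution itself.

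**Truncation.** The stored reference is low by t, uniform on 0 to 1, with E(t) = 0.5 and E(t²) = 1/3. Squared ARMS becomes ARMS² + 2 × 0.5 × mean(d) + 1/3 = ARMS² + mean(d) + 1/3. With mean(d) = 0 the addition is 0.333, or 0.333/0.81 = 41% at 0.9 (√1.1433 = 1.069), 14.8% at 1.5 (√2.5833 = 1.607) and 3.7% at 3.0 (√9.3333 = 3.055). If the app reads low by more than 1/3 BPM on average, truncation lowers ARMS.

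**Effect on the decision, nearest-BPM rounding.** I ran 1,500 simulated trials per setting, with a percentile bootstrap of 1,000 resamples each. At ARMS 1.5 and n = 40 to 55, heavy-tailed and mixture differences moved power by less than 3 points in either direction (for example 0.934 to 0.917, and 0.810 to 0.839). The simulation error of such a difference is about √(2 × 0.82 × 0.18/1500) = 0.014. With normal differences power was 1.000 with and without rounding. At ARMS 0.9 and n = 20 it stayed at or above 0.98.

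**The case against.** The strongest reply is that this hardly matters. Extra error in the reference normally works against the sponsor's own device and so does not manufacture a pass. The scenario that fixed the per-protocol goal is 1.5, where the share is 3.7%, not 10%. Both points stand for rounding to the nearest BPM, and both shares are therefore given. They do not fully cover truncation, whose effect depends on the sign of the app's bias.

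Several stronger readings are tempting but unsupported:

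- *Rounding always raises ARMS.* It does not. If the app PR is also an integer and agreement is very close, the addition can shrink or turn slightly negative. The documents do not state the app's resolution.
- *The trial's ARMS will move from 0.90 to 0.945.* The 0.9 was measured against a fingertip PPG device (SAP 6.1) whose resolution is not given, so it may already include reference rounding. The 10% share of 0.81 is the same either way.
- *Step 5 contradicts the procedure's own precision aim.* The precision argument in section 4 concerns matching the heart rate in time to the app's window, not decimal places. Step 5 sits awkwardly with that effort but does not contradict it.
- *Both endpoint values are exposed to hand-keying errors.* A reader might infer this from "Record the subjects pulse rate in the EDC and then tap the SUBMIT RESULTS button" in the site guide (IVC-400-006g section 7, step 10) and "Output prints hr reference value and saves ecg with annotations as pdf" in Appendix A of IVC-400-006i. For the reference, step 5 says only that the value is entered, not how. The protocol provides a query process, a data management plan and source verification. Section 4.2 step 4 has two people review each rhythm report, and SAP 5.3.1 tabulates differences beyond 6.0 BPM. No separate finding on keying is made.

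Appendix B of IVC-400-006i, which covers validation, is not in the text available to me, so I cannot tell whether it addresses output resolution.

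**Conclusion.** The point holds as a minor one. The reference is reduced to a whole BPM after a finer value has been computed, with no stated rule or reason. Under rounding to the nearest BPM, and independence of rounding error and device difference, this adds 0.083 BPM² to squared ARMS, with the shares tabulated above. The range under nearest-BPM rounding is roughly −0.01 to 0.08 BPM², depending on the app's resolution and how tightly the differences cluster. Truncation would add about 0.33 BPM² if there is no offsetting bias, and would move the Bland-Altman plot by 0.5 BPM. That the value is rounded to nearest is itself an inference; the procedure says only that it is an integer.

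Nothing here threatens the 3.0 BPM criterion, and the effect on pass or fail is negligible. What is gained is a reported ARMS and upper confidence limit that do not carry avoidable reference quantisation.

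**What to change.** Reword IVC-400-006i section 4.2 step 5 along these lines: the script's reference HR is stored to at least 0.1 BPM and is analysed without rounding. Allow one decimal in the eCRF field for the ECG rate. At 0.1 BPM the remaining rounding term is 0.01/12 = 0.0008 BPM², or 0.1% of 0.81. If a whole number is still wanted for display, state the rounding rule and keep that value out of the ARMS calculation.

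The cost is one sentence, one field setting and possibly a change to the script's output format. No extra subjects, visits or measurements are needed. Section 4.1 provides for the ECG files to be kept, so the decimals could also be recovered after collection by re-running the script, provided the app metadata files are kept too.

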Appendix A – Readme

- Create venv with Python 3.9.16
- pip install -r requirements.txt
- Run using command below

`python edan_se301_ra.py file_name_ecg file_name_ivc timezone_name`

where timezone_name is US/Pacific or US/Mountain etc. Output prints hr reference value and saves ecg with annotations as pdf

 INFORMED MINDSET MEDICAL	DOCUMENT VERSION: 1	THIS DOCUMENT SUPERSEDES VERSION: X	PAGE: 8 OF 18
STATUS: Active	TITLE: Rhythm Strip Analysis Procedure for IVC-400-006	IDENTIFICATION: IVC-400-006i	
EFFECTIVE DATE: May 30, 2023	AUTHOR: [name]	APPROVED BY: [name]	

[figure not shown]

Subject ID	MedDRA System Organ Class/ Preferred Term/ Investigator AE Term	Start Date	End Date	Ongoing?	SAE?	Criteria	Severity	Process	Relatio nship	Any	Unanticipated	Caused to Adverse Study Device	Study Discontinu ation
									SAE	Study			
No Data To Report													

ITC = Intent-to-Capture. SAE = Serious Adverse Events.

Program name: 1_16_2_7_1.sas

Run Date: 21NOV2023
